Study Protocol

(Version number: 2.0 Version date: 2025.08.21)

Project Title: Effect of Transcranial Magnetic Stimulation vs Sham Stimulation Combined With Pinaverium Bromide vs Bifidobacteria in Diarrhea-Predominant Irritable Bowel Syndrome: A 2×2 Factorial Randomized Clinical Trial

Sponsor: The First Affiliated Hospital of Soochow University

Responsible Department: Gastroenterology Department

Principal Investigator: [name]

Participating Centers: Xiangcheng People's Hospital of Suzhou, The People's Hospital of Suzhou New District

Investigator Statement and Protocol Signature Page

As the principal investigator of this research project, I hereby commit to adhering to the ethical principles outlined in the National Health Commission's "Ethical Review Measures for Biomedical Research Involving Humans" (2016), the WMA's "Declaration of Helsinki" (2013), the CIOMS's "International Ethical Guidelines for Biomedical Research Involving Human Subjects" (2002), and Good Clinical Practice (GCP). Under the guidance of the Quality Management Standards for Drug Clinical Trials, I will implement the study protocol approved by the Ethics Committee and conduct the research in strict accordance with the requirements of this protocol, ensuring the scientific validity of the study and protecting the health and rights of the subjects.

Name: [name]

Signature:

Date:2025.07.01

Protocol Synopsis

Study objective	(1) To evaluate the alleviating effect of repetitive transcranial magnetic stimulation (rTMS) on chronic visceral pain in patients with diarrhea-predominant irritable bowel syndrome (IBS-D); (2) To assess the interventional effect of pinaverium bromide and bifidobacterium used alone on chronic visceral pain in IBS-D; (3) To analyze potential interactions between the two intervention measures.
Sample size	140
Study population	Patients with diarrhea-predominant irritable bowel syndrome
Study design	Randomized, controlled factorial design study
Inclusion criteria	(1) Age range 18-75 years (either sex) (2) Fulfilling the Rome IV criteria for irritable bowel syndrome diagnosis (3) Bristol stool type 6-7 in >25% and type 1-2 in <25% of bowel movements (4) Patients experienced Bristol stool type 6 or 7 on ≥ 4 days with mean abdominal pain score ≥ 3 during the initial 2-week period
Exclusion criteria	(1) Documented organic gastrointestinal pathology; endocrinologic or metabolic diseases with known gastrointestinal motility effects including diabetes mellitus and hyperthyroidism; previous surgical interventions involving abdominal cavity intestinal tract or anal region (2) current use of any medication with documented effects on gastrointestinal motility or secretory function; administration of concurrent therapies or pharmacologic agents capable of confounding treatment efficacy or safety evaluations (3) pregnancy lactation or postpartum status within 12

	
months
 
(4) noncompliance with randomized treatment allocation or demonstrated poor adherence tendencies

Intervention	
(1) IBS patients receiving rTMS stimulation + pinaverium bromide treatment
 
rTMS stimulation: 1 Hz, 80% MT, 20 min/d, once daily for 2 weeks;
 
Pinaverium bromide: Oral, 3 times daily, 1 tablet/time, for 2 weeks;
 
(2) IBS patients receiving rTMS stimulation + bifidobacterium treatment
 
rTMS stimulation: 1 Hz, 80% MT, 20 min/d, once daily for 2 weeks;
 
Bifidobacterium: Oral, 2 times daily, 4 capsules/time, for 2 weeks;
 
(3) IBS patients receiving sham rTMS + pinaverium bromide treatment
 
Sham rTMS treatment: 0 Hz, 0% MT, 20 min/d, once daily for 2 weeks;
 
Pinaverium bromide: Oral, 3 times daily, 1 tablet/time, for 2 weeks;
 
(4) IBS patients receiving sham rTMS + bifidobacterium treatment
 
Sham rTMS stimulation: 0 Hz, 0% MT, 20 min/d, once daily for 2 weeks;
 
Bifidobacterium: Oral, 2 times daily, 4 capsules/time, for 2 weeks;

Primary endpoint	The primary outcome measure is the proportion of patients achieving a composite response at the end of treatment

	(Week 2), defined as: a reduction of $\geq 30\%$ from baseline in the average daily worst abdominal pain score, and a reduction of $\geq 50\%$ in the number of days with at least one stool consistency meeting BSFS type 6 or 7 criteria during Week 2. Abdominal pain intensity is assessed using an 11-point NRS scale (0-10) for the last 24 hours daily. Stool consistency is recorded daily by the patient selecting the most representative category according to the BSFS.
Secondary endpoints	
1) Anorectal manometry: Record the subject's initial sensation threshold, constant urge sensation threshold, and maximum tolerable volume at baseline (before treatment) and after the end of treatment.
 
2) IBS Symptom Severity Score (IBS-SSS): Evaluated at 1 week, 2 weeks, and 4 weeks after treatment.
 
3) IBS Quality of Life (IBS-QoL) score: Evaluated at 1 week, 2 weeks, and 4 weeks after treatment.

Study timeline	2025.07.1-2026.03.30: Recruit 20-25 patients with diarrhea-predominant IBS meeting Rome IV criteria monthly through multiple centers, using standardized screening procedures (including symptom assessment, exclusion checks, and baseline tests), aiming to complete randomization of 140 cases within 12 months.
Statistical analysis	Use Shapiro-Wilk test to assess normality. Parametric t-test, Wilcoxon rank-sum test, or Kruskal-Wallis test will be used to evaluate continuous data between groups as appropriate.

1. Background

Irritable bowel syndrome (IBS) is a clinically common functional gastrointestinal disorder, affecting 10%-25% of the world's population. The prevalence of IBS in China ranges from 5% to 11%¹. Among patients visiting the gastroenterology specialty outpatient clinic of our hospital, IBS accounts for more than one-third of cases, with diarrhea-predominant IBS (IBS-D) being the most common subtype. Current symptomatic treatments in both Western and traditional Chinese medicine can temporarily alleviate symptoms of intestinal dysmotility. However, these therapies may cause varying degrees of side effects and lack personalized treatment strategies. In Western countries, over 50% of patients turn to complementary and alternative therapies due to insufficient or unstable symptom relief following pharmacological treatment².

A substantial body of literature reports that Transcranial Magnetic Stimulation (TMS) can alleviate chronic visceral hypersensitivity. The specific mechanisms include TMS's ability to modulate cortical excitability, improve cerebral blood flow and metabolism, regulate neurotransmitters and gene expression, as well as induce neural plasticity changes³. Our preliminary basic research identified the claustrum–anterior cingulate cortex neural circuit as a unique pathway regulating chronic visceral hypersensitivity in IBS animal models. Translating this finding to clinical applications, TMS-based modulation of this circuit has been shown to alleviate chronic visceral hypersensitivity in IBS patients⁴. Building on these initial results, the current study aims to further expand the sample size and conduct a multicenter randomized controlled trial to validate the long-term efficacy and safety of rTMS in IBS patients with chronic visceral pain, thereby providing higher-level evidence for its clinical application. As a non-invasive stimulation technique with a favorable safety profile, TMS demonstrates significant therapeutic advantages in clinical practice⁵. Therefore, through this study, we aim to further investigate the clinical efficacy of TMS in treating chronic visceral pain associated with irritable bowel syndrome.

2. Study Objectives

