3.4 Risk and Benefit Rationale

This study adopts a strict risk-benefit assessment system. Potential risks mainly include three aspects: rTMS-related risks (10-15% of subjects may experience transient headache or scalp discomfort, seizure risk <0.1%); pinaverium bromide may cause dry mouth and constipation (incidence about 12%); bifidobacterium may cause mild bloating (incidence 8-10%). Main benefits are reflected in: 1) Clinical level: it is expected that 60% of patients in the combination therapy group will achieve a reduction in abdominal pain VAS score of $\geq 50\%$, and an increase in quality of life score (IBS-QOL) of ≥ 20 points; 2) Long-term benefit: the recurrence rate in the combination group at the 3-month follow-up is significantly lower than in the single-drug groups.

4. Sample Size Calculation

We tested the null hypothesis of no difference in composite response rates between groups. Based on previous literature¹⁸⁻²⁰ and our preliminary trial, assuming a placebo response rate of 23.8%, we expected to double the response rate, assuming a composite response rate for repetitive transcranial magnetic stimulation of 47.61%. At a significance level of $\alpha = 0.05$, 63 patients per group are needed to detect a 23% difference with 80% statistical power. Considering a 10% dropout rate, the final estimated sample size required is 140 patients. [This center will recruit 70 cases, Xiangcheng People's Hospital of Suzhou will recruit 40 cases, and Suzhou New District People's Hospital will recruit 30 cases.

PASS 2021, v21.0.3

2025/7/20 10:54:31 1

Tests for Two Proportions

Numeric Results for Testing Two Proportions using the Z-Test with Pooled Variance
 Hypotheses: H0: P1 - P2 = 0 vs. H1: P1 - P2 ≠ 0

Target Power	Actual Power*	N1	N2	N	P1	P2	Diff D1	Alpha
0.8	0.80393	63	63	126	0.47619	0.2381	0.2381	0.05

* Power was computed using the normal approximation method.

References

 Fleiss, J. L., Levin, B., and Paik, M.C. 2003. Statistical Methods for Rates and Proportions. Third Edition. John Wiley & Sons. New York.

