distributed uniformly by the central pharmacy according to random codes; 2) Statistical unblinding: Unblinding is performed in two stages after database lock -- first, an independent statistician performs inter-group comparisons (Group A vs. B vs. C vs. D), the final reveal of the intervention corresponding to each group occurs after the main conclusions are formed; 3) Quality control: Blinded assessment is conducted monthly, accidental unblinding events must be recorded within 48 hours and the impact on the study assessed.

Rescue Medication and Supportive Therapy (Necessary treatment measures when SAEs related to the study occur)

This study establishes strict norms for rescue medication and supportive therapy: 1) rTMS-related SAE: Seizure - immediately stop stimulation and intravenous push diazepam (5-10mg), transfer persistent convulsions to neurological ICU for monitoring; Severe headache/dizziness - administer paracetamol (≤ 1 g/dose) combined with vestibular inhibitors; 2) Drug-related SAE: Pinaverium bromide allergic reaction - immediately discontinue drug and intramuscular injection of adrenaline (0.3-0.5mg, 1:1000), oral loratadine (10mg/day); Bifidobacterium-induced bacteremia - immediately stop administration and intravenous infusion of vancomycin (15mg/kg q12h) combined with blood culture-guided treatment; 3) Psychological support: Worsening anxiety/depression (HADS score increase ≥ 8 points) - refer to psychological department for intervention. All SAE treatments are executed by the research center's 24-hour emergency team, using standardized (emergency kits) (containing the above drugs and rescue equipment), the treatment process involves continuous ECG monitoring and recording of vital sign changes. Costs of rescue medication are covered by research insurance, subsequent medical follow-up for subjects continues until symptoms completely resolve + 2 weeks. After SAE resolution, the causal relationship with the intervention measures is assessed by an independent medical committee, major SAEs (e.g., anaphylactic shock) require re-evaluation of the individual's risk-benefit ratio for continuing the study. All rescue measures are recorded in the source documents and synchronized to the eCRF system, serving as key data for safety analysis.

6. Study Implementation Procedures

Subject Management

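### Seizure is a named rTMS risk and SAE, but no listed eligibility criterion excludes a patient with a personal history of seizure or epilepsy

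*Protocol*

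**What the plan says.** The hazard is stated twice. Section 3.4 (Risk and Benefit Rationale) gives, among the rTMS-related risks, "seizure risk <0.1" per cent. The rescue-medication text in section 5.2 sets out the response: "rTMS-related SAE: Seizure - immediately stop stimulation and intravenous push diazepam (5-10mg), transfer persistent convulsions to neurological ICU for monitoring". It adds that "the treatment process involves continuous ECG monitoring and recording of vital sign changes".

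The eligibility rules are in the Protocol Synopsis, and section 3.2 repeats the inclusion items. Inclusion covers age, Rome IV diagnosis, stool form, and pain and stool days over the first two weeks. Exclusion has four numbered items:

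- (1) organic gut disease, endocrine or metabolic disease affecting motility, and abdominal or anal surgery;
- (2) drugs acting on the gut, and "administration of concurrent therapies or pharmacologic agents capable of confounding treatment efficacy or safety evaluations";
- (3) pregnancy, lactation and the postpartum year;
- (4) poor adherence.

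The Synopsis timeline refers to "standardized screening procedures (including symptom assessment, exclusion checks, and baseline tests" but does not say what these contain. The Investigator Statement gives a general undertaking to work in "strict accordance with the requirements of this protocol, ensuring the scientific validity of the study and protecting the health and rights of the subjects".

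**The concern.** A protocol that identifies a serious harm of its own intervention would normally keep out the patients in whom that harm is most to be feared. Here the information is used only to plan rescue, which begins once a seizure has occurred, and not to select patients.

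What is at stake is patient safety in the two active-stimulation arms, and consistency. Three centres recruit, and without a written rule each may decide differently about the same patient. If a seizure history comes to light after randomisation, the centre must either stimulate the patient or withhold the allocated treatment from someone already in the trial.

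**Working it through.** **1. Does any listed criterion reach a patient with a past or untreated seizure condition?**

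- Inclusion criteria (Synopsis and section 3.2): nothing neurological.
- Exclusion (1): gut, endocrine/metabolic and surgical history only.
- Exclusion (2): therapies and drugs being given. A patient on an anti-seizure drug might be excluded if that drug is judged to confound the evaluation. A patient who takes nothing is not covered.
- Exclusions (3) and (4): not relevant.
- Investigator discretion to exclude on safety grounds: no such item is listed.

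No listed criterion excludes this patient.

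**2. What scale of seizure risk does the protocol itself imply?**

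Inputs: the section 3.4 ceiling of 0.1%, read as a risk per patient (assumption), and 140 patients with half on active stimulation (equal allocation assumed), so 140 / 2 = 70.

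- Expected seizures: at most 70 × 0.001 = 0.07.
- Chance of at least one: at most 1 − 0.999^70 = 0.068, or 6.8%.

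This is the background ceiling the protocol accepts. It does not measure the omission: the protocol does not say which population the rate describes, gives no rate for patients with a seizure history, and gives no prevalence of such a history.

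**3. Would the extra exclusion affect the sample size?**

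The plan's figure is first reproduced from section 4, with p1 = 0.47619, p2 = 0.23810, mean 0.35714, two-sided alpha 0.05, power 0.80 and a pooled Z-test:

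- n = [1.960 × √(2 × 0.35714 × 0.64286) + 0.842 × √(0.47619 × 0.52381 + 0.23810 × 0.76190)]² / 0.23810²
- = (1.328 + 0.552)² / 0.0567 ≈ 62.4, so 63 per group, with power 0.804.
- Inflated for 10% dropout: 126 / 0.90 = 140.

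The target counts randomised patients. Candidates excluded at screening are replaced before randomisation, so 140 and the power stand.

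**4. What does each excluded candidate cost in recruitment time?**

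The Synopsis gives a monthly rate of 20 to 25 and also speaks of "aiming to complete randomization of 140 cases within 12 months", which is 140 / 12 = 11.7 per month. At the fastest rate one replacement takes 30.44 / 25 = 1.2 days; at the slowest, 30.44 / 11.7 = 2.6 days.

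**The case against.** **The link from seizure history to added risk is not in the protocol.** This stands as a limit on the point. The Background credits TMS with the "ability to modulate cortical excitability" but gives no direction of effect on seizure risk, and the regimen is low-frequency and below motor threshold. No section calls a seizure history a contraindication. The starting point is nevertheless the protocol's own: it judged seizure worth naming and planning for at this regimen, and it offers no argument for leaving the history out of the criteria.

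**Other safeguards may exist.** A reader might infer that only the general undertaking in the Investigator Statement stands between such a patient and stimulation. The text does not support that. The screening checks and baseline tests are not described, so a seizure question may be asked, and the consent form, which was not available, may carry rTMS precautions. Neither would be a listed eligibility criterion, and the undertaking itself ties the investigator to the protocol as written.

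**Rescue is well planned.** It is: a specific seizure plan, a 24-hour emergency team and ECG monitoring. This limits the consequences of a seizure but not its occurrence.

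**This could be left to the SAP.** It could not; eligibility belongs in the protocol.

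**Conclusion.** The omission is real and should be corrected. The listed criteria admit a patient with a past or untreated seizure condition to a trial in which seizure is a named risk of the intervention. The grading is a recommended safety improvement, with medium confidence, because the added risk at this dose rests on clinical judgement and has no size in the document.

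Three stronger readings should be avoided:

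- **The protocol contradicts itself.** It does not. The safety text and the eligibility list are compatible; the list is incomplete.
- **The 0.07 expected seizures, or 6.8%, is the price of the gap.** It is the background ceiling under the assumptions shown in the working, and it says nothing about the excess.
- **A known number of patients has already been exposed.** One might multiply the planned monthly rate by the time from the planned start to the date of version 2.0. The document does not say whether recruitment had begun, or whether the rate counts entry to the two-week run-in or randomisation. The number enrolled is not in the document.

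**What to change.** Add the exclusion: personal history of seizure or epilepsy. Check it with one screening question before randomisation, applied identically in all four arms and all three centres, and put the same question to any patients already enrolled. Whether further rTMS-specific exclusions are needed is for the responsible clinicians.

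The cost is a protocol amendment with ethics approval, one screening question, and a few candidates lost before randomisation. Their number is not in the document; each takes about 1.2 to 2.6 days of recruitment to replace. The analysis is untouched.

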2.1 Primary Objectives

- (1) To evaluate the alleviating effect of repetitive transcranial magnetic stimulation (rTMS) on chronic visceral pain in patients with diarrhea-predominant irritable bowel syndrome (IBS-D); (2) To assess the interventional effect of pinaverium bromide and bifidobacterium used alone on

chronic visceral pain in IBS-D; (3) To analyze potential interactions between the two intervention measures.

3. Rationale

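### The tests named for continuous endpoints do not estimate the rTMS-by-drug interaction that the protocol lists as an objective, nor adjust for the manometry baseline it collects

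*Protocol*

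**What the plan says.** The statistical analysis row of the protocol synopsis prescribes a Shapiro-Wilk check and then: "Parametric t-test, Wilcoxon rank-sum test, or Kruskal-Wallis test will be used to evaluate continuous data between groups as appropriate". Section 7 adds no model. No SAP is at hand.

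The design is a 2×2 factorial, rTMS or sham crossed with pinaverium or bifidobacterium. The third item in section 2.1, under primary objectives, reads "To analyze potential interactions between the two intervention measures". It is not tied to an endpoint.

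The continuous endpoints are all secondary. Manometry is recorded with "maximum tolerable volume at baseline (before treatment) and after the end of treatment". The two questionnaires list follow-up times only: "IBS Symptom Severity Score (IBS-SSS): Evaluated at 1 week, 2 weeks, and 4 weeks after treatment" and "IBS Quality of Life (IBS-QoL) score: Evaluated at 1 week, 2 weeks, and 4 weeks after treatment". Section 3.4 nevertheless expects IBS-QOL to rise by at least 20 points. The study timeline row describes recruitment "using standardized screening procedures (including symptom assessment, exclusion checks, and baseline tests"), without naming an instrument.

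On blinding, section 5.2 says that after database lock "an independent statistician performs inter-group comparisons (Group A vs. B vs. C vs. D"), and that "the final reveal of the intervention corresponding to each group occurs after the main conclusions are formed".

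**The concern.** An interaction in a 2×2 trial is a difference of differences: the rTMS effect with pinaverium minus the rTMS effect with bifidobacterium. The named tests answer other questions. A t or Wilcoxon test on a factor margin addresses one main effect. Kruskal-Wallis across four arms asks whether any arm differs and does not say why. None of these yields an interaction estimate with a confidence interval.

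The named tests also take no covariate, so as worded the manometry baseline does not enter the analysis. A test on change scores would use it, but the protocol does not mention change scores, and in large samples they are never more precise than ANCOVA.

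At stake are an unanswered objective for the continuous endpoints and some lost precision. Bias is not at issue, because allocation is randomised.

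**Working it through.** **The plan's own figure.** Section 4 gives P1 = 0.47619, P2 = 0.2381, 63 per group, two-sided α = 0.05 and a pooled Z-test. The mean proportion is 0.35714.
- SE under the null: √(2 × 0.35714 × 0.64286 / 63) = 0.0854.
- SE under the alternative: √((0.47619 × 0.52381 + 0.2381 × 0.7619) / 63) = 0.0827.
- Power: Φ((0.2381 − 1.96 × 0.0854) / 0.0827) = Φ(0.856) = 0.804, against the stated 0.80393.
- Enrolment: 126 / 0.9 = 140.

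The figures reproduce. They size one two-group contrast on the binary primary endpoint and do not address an interaction.

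**Detectable effects on a continuous endpoint.** The protocol gives no SD or continuous effect size, so results are in SD units. With 126 evaluable (31.5 per arm on average), 80% power and two-sided 0.05, the multiplier is 1.96 + 0.842 = 2.80.
- Main effect on the margin: SE √(4/126) = 0.178; detectable 0.50 SD.
- Interaction: SE √(16/126) = 0.356; detectable 1.00 SD.
- Power for an interaction of 0.50 SD: Φ(0.50/0.356 − 1.96) = about 29%.

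**Use of baseline.** The baseline-outcome correlation ρ is an assumption. The unadjusted SE is multiplied by √(1 − ρ²) for ANCOVA and by √(2(1 − ρ)) for a change score.

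| ρ | ANCOVA factor | Change factor | Interaction: ANCOVA / change (SD) | Main effect: ANCOVA / change (SD) |
|---|---|---|---|---|
| 0.3 | 0.954 | 1.183 | 0.95 / 1.18 | 0.48 / 0.59 |
| 0.5 | 0.866 | 1.000 | 0.86 / 1.00 | 0.43 / 0.50 |
| 0.7 | 0.714 | 0.775 | 0.71 / 0.77 | 0.36 / 0.39 |

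**What each test responds to.** In simulation (arms of 32/31/31/32, SD 1, two-sided 0.05), two patterns were compared, with arms ordered rTMS+pinaverium, rTMS+bifidobacterium, sham+pinaverium, sham+bifidobacterium:
- a pure rTMS effect, means 0.5, 0.5, 0, 0;
- a pure crossover, means 0.25, −0.25, −0.25, 0.25, so the interaction contrast is 4 × 0.25 = 1.0 SD.

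The skewed data are lognormal (sigma 0.5, scaled to SD 1). Shapiro-Wilk gave p < 0.05 in at least one arm in 99.5% of those runs, so the plan's normality step would point to rank tests. Percentages are approximate rejection rates.

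| Data | Test | Pure rTMS effect | Pure crossover |
|---|---|---|---|
| Normal | Kruskal-Wallis | 60% | 60% |
| Normal | t-test on rTMS margin | 78% | 4% |
| Normal | Interaction term in linear model | 5% | 80% |
| Skewed | Kruskal-Wallis | 82% | 82% |
| Skewed | Wilcoxon on rTMS margin | 93% | 4% |
| Skewed | Interaction term in linear model | 5% | 80% |
| Skewed | rTMS main effect in unadjusted linear model | 80% | 5% |

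The equal Kruskal-Wallis rates arise because both patterns spread the arm means equally, and that test sees only the spread. The model's interaction term separates the patterns, and its 95% CI covered the true value in 95% of runs. On raw skewed data, however, the unadjusted linear model gives up about 13 points of main-effect power to Wilcoxon (93% − 80%).

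**Masked analysis.** Four letters can be paired in three ways: AB|CD, AC|BD and AD|BC. One pairing is the rTMS effect, one the drug effect and one carries the interaction. All three can be computed from the letters, but which is which is unknown until the reveal.

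**The case against.** The strongest reply is that this is one line of a synopsis, limited to continuous data and qualified by its closing words, and that models belong in an SAP not shown here. The interaction may be meant for the binary primary endpoint, which the sentence does not govern. Much of this is fair. An SAP could add both the interaction model and the covariate, and baseline adjustment is a gain in precision whose size depends on an assumed correlation. What stands is that the protocol did choose tests, and those tests do not serve an objective that it lists without limiting it to the primary endpoint. A t-test on the diagonal pairing of arms would target half the interaction contrast, but nothing in the protocol suggests that use.

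It can also be said that a linear model costs power when data are skewed. That is correct, as the table shows, and it shapes the fix. So is the remark that the interaction will be poorly estimated at this size. That is a reason to report it with its interval and not lean on its p-value.

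A reader might infer that the four-letter code makes a factorial analysis impossible before the reveal. It does not: every contrast can be computed and only the labels are missing. A reader might also infer six unadjusted pairwise comparisons with inflated error, but the protocol does not propose them.

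**Conclusion.** The point holds as a mismatch between a listed objective and the methods named for continuous endpoints, together with an unused manometry baseline. It is worth correcting but limited: only secondary endpoints are affected, t and Wilcoxon tests on the margins remain valid for main effects, and randomised comparisons are unbiased. The detectable interaction is about 1.00 SD unadjusted, or 0.95, 0.86 and 0.71 SD with ANCOVA at ρ = 0.3, 0.5 and 0.7. These figures rest on 126 evaluable patients, equal arms and assumed correlations; the simulated effects and lognormal shape are also assumptions.

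A reader might infer that IBS-SSS and IBS-QoL are not measured before treatment. The protocol does not show that. No pre-treatment time is listed, but the unspecified baseline tests may include them, and the IBS-QOL rise expected in section 3.4 suggests that a starting value is intended. This is a minor item to confirm, although a score that was never taken could not be recovered by any later SAP.

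**What to change.** 1. Replace the synopsis sentence, or point it to an SAP that does the following. For each continuous secondary endpoint, fit a linear model with rTMS, drug and the baseline value where collected, using a mixed model for the repeated scores. Report both main effects with 95% CI. Then add the rTMS-by-drug term and report it with its 95% CI, described as an imprecise estimate.
2. For skewed outcomes, keep the marginal Wilcoxon test for the main effects, or fit the model to transformed or rank-transformed values and state that the interaction then refers to that scale.
3. In section 5.2, consider giving the statistician two masked factor codes, such as X/Y and P/Q, in place of A to D. The interaction could then be told from the main effects before the reveal. The price is slightly less masking, so this is a choice to weigh.
4. Confirm that IBS-SSS and IBS-QoL are recorded at screening, and list that time point.

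The cost is analysis wording, a change of coding if wanted and, only if not already done, two questionnaires once per patient. Sample size, treatment and the manometry schedule are unchanged.
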